Going Protocol title

**Pilot randomized control trial of smartphone-enabled breath alcohol monitoring on perceived fitness to drive a vehicle among intoxicated adults**

Short Title BrAC monitoring and Perceived Fitness to Drive Among Intoxicated Adults

Brief description of the protocol Please provide, in 500 characters or less, a description of the purpose of the study, the targeted population and the procedures/interactions/interventions necessary for participation.

The **goal of this study** is to conduct a laboratory-based pilot randomized control trial of smartphone-enabled breath alcohol monitoring on perceived fitness to drive a vehicle among intoxicated adults. We will enroll up to 30 adults aged  $\geq 21$ -44 who are frequent drinkers without dependence who drive more than four times per week to complete a standardized alcohol drinking protocol in a monitored setting collecting breathalyzer measurements. The protocol involves consuming three weight-based doses of alcohol with a target BAC of 0.10 and completing breathalyzer measurements every 20 minutes until a BAC of 0.03 is reached. The control group would complete a visual analog scale on their perceived fitness to drive and be blinded to their breath alcohol readings with the BACtrack Mobile Pro device, while the intervention group would do the same, but be shown their breath alcohol readings on the paired BACtrack smartphone application. Our previous research has validated the accuracy of the BACtrack Mobile Pro device to measure BAC within  $+$ / $- 0.001$  of police-grade breathalyzer and estimate BAC within  $+$ / $- 0.01$  of a blood test.

Submission type

Social and Behavioral Sciences

Is this a response to an already submitted Initial Review? NO

Human Source Material\*Does this research include collection or use of human source material (i.e., human blood, blood products, tissues or body fluids)? No

Does the research proposal involve the use and disclosure of research subject's medical information for research purposes? NO

CTRC Resources: Does the research involve CTRC resources? YES

Pathology and Laboratory Medicine Resources\*

Will samples be collected by hospital phlebotomy and/or processed or analyzed by any of the clinical laboratories of the University of Pennsylvania Health System? NO

Does this research involve collection of blood products in the Penn Donor Center and/or the use of apheresis for treatment or collection of cells or other blood components? NO

Research involving blood transfusion or drug infusions\* NO

Will your research involve blood transfusion or infusion of study drug in 3 Ravdin Apheresis Unit for research purposes? **NO**

Trial in Radiation Oncology. Is this research a prospective trial being done in Radiation Oncology, and if so, has this protocol been approved by the Radiation Oncology Protocol committee? **NO**

Does your study require the use of University of Pennsylvania Health System (UPHS) services, tests or procedures\*, whether considered routine care or strictly for research purposes? (UPHS includes all Penn hospitals and clinical practices, including the Clinical Care Associates network of community practices). Examples of UPHS services/tests/procedures includes the Clinical Translational Research Center (CTRC), laboratory tests, use of the pathology lab, cardiovascular imaging tests or radiology imaging tests (whether being billed via the Service Center or through UPHS), other diagnostic tests & procedures and associated professional services, etc.

**YES**

Primary Focus The primary focus of your research is best described by which of the following (single best answer):

Tissue/biospecimen

Research on human data sets (e.g. medical records, clinical registries, existing research data sets, medical administrative data, etc.)

Epidemiological research

Survey research (the main focus of the research is administration of a survey to research subjects)

**Sociobehavioral (i.e. observational or interventional)**

Mechanistic or physiologic study in human subjects (T1 Translational research in humans or Phase I drug research)

Clinical Trial (prospectively assigning subjects to health-related interventions to evaluate outcomes)

Quality Improvement research (assessment of clinical care practices to enhance patient care)

Other

Protocol Interventions: Does your protocol require any of the following interventions? Check all that apply.

**Sociobehavioral (i.e. cognitive or behavioral therapy)**

Drug

Device - therapeutic

Device - diagnostic (assessing a device for sensitivity or specificity in disease diagnosis)

Surgical

Diagnostic test/procedure (research-related diagnostic test or procedure)

Obtaining human tissue for basic research or biospecimen bank

**Survey**

None of the above

Business Administrator

Name **[name]**

Department/School/Division **Emergency Medicine**

[contact]

[contact]

Pager

Email [contact]

[Department budget code](#)

[Funding Sponsors:](#) (internal pilot) University of Pennsylvania Injury Science Center

[Project Funding](#)

[Is this project funded by or associated with a grant or contract?](#) Yes

[Study Instruments:](#)

1. Intake Survey (attached to the protocol)

a) Driving History and Experience Questionnaire DHEQ (Harrison & Fillmore, 2005) This self-report questionnaire gathered information on driving history and behaviors. Included in the questionnaire are measures of driving experience such as length of time holding a driver's license and number of days and miles driven per week. The questionnaire also gathered information about participants driving behaviors, such as license revocations, presence and number of DUI citations and punishments, traffic accidents, traffic tickets, typical driving environment (rural, urban, and interstate), and the type of vehicle transmission (manual, automatic, or both).

b.) Drinking and driving questionnaire (McCarthy et al) This self-report questionnaire gathered information on individuals drinking and driving history. The questionnaire asked participants to respond to questions about drinking and driving history on 4 or 5 point Likert scales. The questionnaire included a measure of frequency of drinking and driving and typical quantity of alcohol consumed before driving. The items were obtained from a scale reported by McCarthy et al. (2012).

2. Decision making survey (attached to the protocol)

a). the Delayed discounting questionnaire (Senecal et al 2012).

b). Barratt Impulsiveness Scale BIS-11 (Patton et al., 1995) This 30-item self-report questionnaire is designed to measure the personality dimension of impulsivity. Participants rated 30 different statements on a 4-point Likert-type scale ranging from Rarely/Never to Almost Always/Always. Higher total scores indicate higher levels of self-reported impulsiveness (score range 30-120).

3. Self-Reported intoxication Survey (attached to the protocol): Includes visual analogue scales which measure self reports of

a) Perceived Driver Fitness (Van Dyke and Fillmore 2014)

b) Perceived intoxication and BAC estimation.(Harrison and Fillmore 2005; Harrison et al 2007)

4. Smartphone Breathalyzer (BACTrack Mobile Pro). Our previous research (IRB protocol # XXX) has validated the accuracy of the BACtrack Mobile Pro device to measure BAC within +/- 0.001 of police-grade breathalyzer and estimate BAC within +/- 0.01 of a blood test. This work has been submitted as an abstract to a national meeting on injury prevention and will be submitted in next two months for peer-reviewed publication. (<https://www.bactrack.com/products/bactrack-mobile-smartphone-breathalyzer?gclid=CNi55bygNMCFZyPswodb7sNOg&mkwid=&pcrid=104045623957&pdv=m&pkw=&pmt=&ring-central=google-ppc>).

5. Bactrack Skyn: Bactrack skyn is a wearable device that tracks breath alcohol content. A portion of participants will be selected to wear these devices in order to validate their ability to measure and estimate blood alcohol content. (<https://www.bactrack.com/pages/bactrack-skyn-wearable-alcohol-monitor>).

Arm 1 (Control): Participants randomized to this arm will consume three weight-based doses of alcohol with a target BAC of 0.10 and complete breathalyzer measurements every 20 minutes until a BAC of 0.03 is reached. They will complete a visual analog scale (the Self-Reported intoxication Survey) on their perceived fitness to drive and be blinded to their breath alcohol readings with the BACtrack Mobile Pro device.

Arm 2 (Intervention): Participants randomized to this arm will consume three weight-based doses of alcohol with a target BAC of 0.10 and complete breathalyzer measurements every 20 minutes until a BAC of 0.03 is reached. They will be shown their breath alcohol readings with the BACtrack Mobile Pro device before completing a visual analog scale (the Self-Reported intoxication Survey) on their perceived fitness to drive.

Because of the limited availability of the Bactrack Skyn measurement tool in our previous trial (please reference IRB #825273, “Reducing Risky Drinking using Smartphone Paired Breathalyzer”), we will continue to test the validity of this device with the BacTrack Mobile Pro breathalyzer throughout this protocol.

Method for Assigning Subjects to Groups: Describe how subjects will be randomized to groups.

All participants who meet eligibility criteria and provide written consent will then be randomized at the time of study enrollment using block randomization.

Administration of Surveys and/or Process\*: Describe the approximate time and frequency for administering surveys For surveys, questionnaires and evaluations presented to groups and in settings such as high schools, focus group sessions or community treatment centers explain how the process will be administered and who will oversee the process. For instance, discuss the potential issues of having teachers and other school personnel administer instruments to minors who are students especially if the content is sensitive in nature. Describe the procedure for audio and videotaping individual interviews and/or focus groups and the storage of the tapes. For instance, if audio tape recording is to be used in a classroom setting, describe how this will be managed if individuals in the class are not participating in

the study. Explain if the research involves the review of records (including public databases or registries) with identifiable private information. If so, describe the type of information gathered from the records and if identifiers will be collected and retained with the data after it is retrieved. Describe the kinds of identifiers to be obtained, (i.e. names, social security numbers) and how long the identifiers will be retained and justification for use and/or evaluations.

We are planning to recruit and enroll up to 30 participants through recruitment material that will be sent out through email and posted on fliers (see recruitment material attached). Inclusion criteria will be: (a) age 21-39 years old, (b) less than 4 drinking days and less than 12 drinks per week on average in the past 2 months, (c) have consumed at least 4(women) or 5 (men) drinks on one occasion, in the past year without experiencing adverse effects (c) a valid photo ID (d) willing and able to use a rideshare credit or septa token as transportation home from the study visit. Exclusion criteria will be (a) desire alcohol treatment now or received it in the past 6 months, (b) alcohol use disorder with withdrawal per DSM-V criteria and (c) non-English-speaking, and (d) women who are pregnant (e) individuals who should not consume alcohol due to a medical condition. Individuals, who are interested in the study, will be contacted and screened over the telephone using our Alcohol Study Screener (attached to this protocol). All participants who meet inclusion criteria will be invited to consent to the study.

Interested participants will call the study hotline where an IRB-approved research assistant or project manager, will answer any questions, administer the study screening and go over the written informed consent. There will be an optional in person study visit for the participant to come in and review study procedures, and sign written informed consent, in person. At the study visit, which occurs at a predetermined time, the participant will first sign written informed consent to participate. They will then take an initial survey, with questions related to their past alcohol use and habits including Driving History and Experience Questionnaire DHEQ1, Drinking and Driving Questionnaire. Participants will also take the Decision making survey, which includes The Barratt Impulsiveness Scale, and the Delayed discounting questionnaire.

Some participants will wear the BACtrack Skyn wrist device, which will start collecting alcohol measurements after the first dose of alcohol. Participants will then receive three doses of vodka mixed with juice based on their gender and weight designed to reach a peak blood alcohol level of .10 g/dL. After each dose, their Breath Alcohol Content (BrAC) will be measured using the BacTrack Mobile device. After each breathalyzer measurement, participants will receive the Self-Report of Intoxication Survey, which will include Perceived Driver Fitness and Perceived intoxication and BAC estimation, which are measured using a visual analogue scale.

For the control group, participants will remain blinded to the BrAC readings on the BacTrack mobile app. For the intervention group, the participants will be shown their BrAC readings on the BacTrack mobile app before completing their Self-Report of Intoxication Survey.

Besides a preliminary study visit for participants to consent to the study and complete the eligibility survey, all research activities will take place in one of the four CTRC study sites and will occur in a study session of approximately six hours in length with up to four participants at each session. Participants will be separated into different research rooms at the CTRC.

Data collection will include contact information, medical history, and history of alcohol use, various measurements of Breath Alcohol Content (BrAC), as well as survey data from the self-reported

intoxication survey. The informed consent process during study enrollment will describe all of these aspects of data collection.

Attached to this protocol are the following study instruments for data collection and recruitment:

1. Written Informed Consent
2. Screening Survey
3. Eligibility Survey
4. Intake Survey
5. Decision making survey
6. Self-Reported intoxication Survey

Describe how and who manages confidential data, including how and where it will be stored and analyzed. For instance, describe if paper or electronic report forms will be used, how corrections to the report form will be made, how data will be entered into any database, and the person(s) responsible for creating and maintaining the research database. Describe the use of pseudonyms, code numbers and how listing of such identifiers will be kept separate from the research data.

Paper forms will be used to collect data and a research assistant will create and maintain the research database. All source documents will be identified by study identification (ID) number, and the key to that ID number will be kept in a locked file cabinet. All personally identifiable information also will be kept separately in a locked file cabinet. No results will be reported in a personally identifiable manner. All tracking system data and research database information will be password-protected with several levels of protection: first, a password will be required to access the computer of the user who has access to the database; second, a password will be required to access the database.

#### Abstract\*

In the last two years, personal breathalyzers that pair with smartphones have appeared on the market, allowing individuals to monitor and track their own Breath Alcohol Content (BrAC). We are in the midst of completing a laboratory based validation study of the test accuracy of six of these devices relative to a police-grade breathalyzer and blood alcohol content (BAC) levels. Our preliminary data from our first 10 participants indicate that at least 2 of the 6 devices (Alcohoot and BACtrack Mobile Pro) are highly accurate within +/- 0.01 of police grade breathalyzers and BAC levels. The next logical step in determining how these devices can be leveraged to reduce drinking and driving is to determine whether knowing one's breath alcohol content in real-time affects the likelihood of driving among intoxicated individuals. In the U.S., it is illegal to drive with a BAC of 0.08 or higher. However, driving is impaired at BACs of 0.04 or higher and some countries impose a stricter illegal BAC limits (e.g. 0.05 or higher). Therefore, while it is hoped that the use of personal breathalyzers may reduce the risk of driving impaired by taking the guesswork out of estimating one's BAC, there is the possibility that some individuals may be more likely to drive if their measured BrAC is less than 0.08 even if they feel intoxicated.

#### Overall objectives:

Given the popularity of these devices and the ability to share these data in a secure and automated fashion, if reliable, these devices could be used for implementing strategies to reduce risky drinking on a much broader scale than previously possible. Contingency management is the systematic use of behavioral rewards or disincentives to reinforce desired behaviors, and shows promise as one of the most effective means of prevention of drug and alcohol abuse. By using automated remote monitoring, innovative contingency management strategies incorporating insights from behavioral economics could be more easily implemented by providing immediate rewards and feedback and by taking advantage of group-based incentives and norms. Our preliminary data from our first 10 participants indicate that at least 2 of the 6 devices are highly accurate within +/- 0.01 of police grade breathalyzers and BAC levels. Because our long-term objective is to leverage smartphone-paired breathalyzers to implement cost-effective and scalable behavioral interventions to reduce risky drinking behaviors such as drinking and driving, the next logical step is to determine whether knowing one's breath alcohol content in real-time affects the likelihood of driving among intoxicated individuals.

Primary outcome variable:

Perceived fitness to drive on a visual analog scale, repeated every 20 minutes. We will test the hypothesis that those shown the BraC reading vs. those blinded to the BraC reading have lowered perceived fitness to drive for BACs > 0.05.

Secondary outcome variables:

Secondary outcomes: We will conduct descriptive analyses of the association between self-reported measures of intoxication, predicted blood alcohol content, driving fitness, and willingness to drive with measured breath alcohol content by device. We will also explore the effect modification of these by self-reported measures of impulsivity and delayed discounting.

Background: Describe succinctly and clearly the past findings which justify the plan for this project. A summary of the relevant literature in the area of interest and reports of previous studies should be included.

Nearly 88,000 people die annually from alcohol-related causes, making it the third leading cause of preventable death in the US.(National Institute on Alcohol Abuse and Alcoholism, 2015) Excessive alcohol consumption is a major risk factor for injury, assault, and suicide.(Easton, C.J., Swan, S., & Sinha, 2000; McNeill, Sherwood, Starck, & Thompson, 1998; White & Hingson, 2014) In 2013, 10,076 people were killed in drinking and driving-related motor vehicle crashes, accounting for one-third of all driving-related deaths.(National Highway Traffic Safety Administration, 2015) Individuals who engage in drinking and driving, compared to those do not, have similar cognitive abilities, actually understand legal consequences *better*, but are *poorer* planners and *more present-biased*, heavily weighing immediate costs and benefits relative to future ones when making decisions.(Sloan, Eldred, & Xu, 2014) This suggests that strategies such as planning a designated driver and providing immediate reinforcement of the benefit of moderating alcohol consumption are particularly promising approaches to reduce drinking and driving and binge drinking. Nationally, 17% of individuals aged 18 and older report binge drinking in the past month.(Centers for Disease Control and Prevention, 2015; Substance Abuse and Mental Health Services Administration, 2015) Importantly, binge drinkers are 14 times more likely to report alcohol-impaired driving than non-binge drinkers.(Naimi et al., 2003)

Contingency management, the systematic use of behavioral rewards or disincentives to reinforce desired behaviors, is one of the most effective approaches to reduce drug use,(Alessi & Petry, 2013; Kosten & O'Connor, 2003; N. M. Petry, 2000; Prendergast, Podus, Finney, Greenwell, & Roll, 2006; Roll et al., 2006) likely because heavy substance abusers are consistently more present biased.(MacKillop et al., 2011) Our prior work demonstrates the effectiveness of contingency management among dependent drinkers using daily visits to a treatment center.(Nancy M Petry, Martin, Cooney, & Kranzler, 2000) The effectiveness of contingency management relies on readily being able to detect substance use. However, alcohol is metabolized more quickly than most drugs, making it difficult to monitor in the community. In the last two years, breathalyzers that pair with smartphones have come on the market,(“Alcohoot Smartphone Breathalyzer,” n.d., “BACtrack Mobile Pro,” n.d.; Drivesafe Evoc, n.d. “Floome: Smartphone Breathalyzer,” n.d; “DrinkMate,” n.d; “BACtrack Ultra-Portable Personal Keychain Breathalyzer,” n.d) allowing individuals to monitor and more easily track their own breath alcohol concentration (BrAC). Given the popularity of these devices,(“A smartphone breathalyzer,” 2015; Jolly, 2015) booming sales (an \$816 million dollar market),(Wintergreen Research, 2016) and the ability to share the data they generate in a secure and automated fashion, the devices could be used to implement contingency management strategies to reduce risky drinking on a much broader scale. These could be combined with contingency management strategies that incorporate insights from *behavioral economics* to provide immediate rewards and feedback and take advantage of group-based incentives and norms.(Loewenstein et al., 2007; MS et al., 2015)

In the last two years, three companies have begun to sell breathalyzers that pair with smartphones, allowing individuals to monitor and track their own Breath Alcohol Content (BrAC). Given the popularity of these devices, and the ability to share these data in a secure and automated fashion, if reliable, these devices could be used for implementing contingency management strategies to reduce risky drinking on a much broader scale than previously possible. Furthermore, by using automated remote monitoring, innovative contingency management strategies incorporating insights from behavioral economics could be more easily implemented by providing immediate rewards and feedback and by taking advantage of group-based incentives and norms. However the validity of smartphone-paired breathalyzer measurements has not been independently confirmed in the peer-reviewed literature, impeding further research application and funding. Informal assessments by the national media suggest that commercial smartphone paired breathalyzers may vary in reliability. Our preliminary data from our first 10 participants indicate that at least 2 of the 6 devices are highly accurate within +/- 0.01 of police grade breathalyzers and BAC levels. Now that we have an understanding of the reliability of these technologies in measuring breath alcohol content, it's important to determine whether knowing one's breath alcohol content in real-time affects the likelihood of driving among intoxicated individuals to further so we can more effectively develop behavioral intervention strategies..

A smartphone breathalyzer. (2015). Retrieved January 4, 2016, from  
<http://www.usatoday.com/videos/tech/2013/05/19/2216497/>

Alcohoot Smartphone Breathalyzer. (n.d.). Retrieved December 24, 2015, from  
<http://alcohoot.com/products/alcohoot-breathalyzer>

Alessi, S. M., & Petry, N. M. (2013). A randomized study of cellphone technology to reinforce alcohol abstinence in the natural environment. *Addiction (Abingdon, England)*, 108(5), 900–9.  
<http://doi.org/10.1111/add.12093>

BACtrack Mobile Pro. (n.d.). Retrieved December 24, 2015, from  
<http://www.bactrack.com/products/bactrack-mobile->

breathalyzer?gclid=Cj0KEQiAzO6zBRC25Ju1idGJiZkBEiQAP3Sf6MVZKaULJEmXCJnBqqXvqrzfuiYe3hpIEsgMir1\_QXUaAl\_o8P8HAQ

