175 minutes	
 
Measurement of BrAC with BacTrack mobile breathalyzer
 
Control: Blinded to BrAC reading. Intervention: Shown BrAC reading on BacTrack mobile app
 
Self Report of Intoxication Rating Survey:
 

190 minutes	
 
Measurement of BrAC with BacTrack mobile breathalyzer
 
Control: Blinded to BrAC reading. Intervention: Shown BrAC reading on BacTrack mobile app
 
Self Report of Intoxication Rating Survey:
 

205 minutes until study completion	
 
Measurement of BrAC with BacTrack mobile breathalyzer
 
Control: Blinded to BrAC reading. Intervention: Shown BrAC reading on BacTrack mobile app
 
Self Report of Intoxication Rating Survey:
 
Breathalyzer measurements will be obtained until participant is at .03 or lower
 

Deception: Does your project use deception?

NO

Deception could be considered any direct misinformation presented to the subject or omission of key information pertaining to the design or nature of the project.

NO

Are you conducting research outside of the United States? \*

NO

Analysis Plan: Describe briefly the statistical methods used to analyze the data

Data analysis will be led by [name], Professor of Biostatistics.

Primary outcome:

We will test for differences in perceived fitness to drive according intervention arm and BrAC level accounting for clustering of measurements within participants and time from the first drink using a generalized linear model with a logit link. We will then explore the mediating effects of baseline demographic and psychological variables with inclusion of these variables in the model.

**Secondary outcomes:** We will conduct descriptive analyses exploring the effect modification of baseline demographic and psychological measures on these differences including: age, sex, BMI, past level of alcohol consumption, delay discounting rate, and the Barrat's impulsivity scale.

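### Must the plan state how randomised arm enters the secondary associations of self-reports with measured BrAC, given that one arm answers after seeing the reading?

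*Combined protocol and SAP*

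**What the plan says.** Under Overall objectives, the Secondary outcome variables paragraph promises a descriptive treatment of one group of relations: "association between self-reported measures of intoxication, predicted blood alcohol content, driving fitness, and willingness to drive with measured breath alcohol content by device". It then adds: "We will also explore the effect modification of these by self-reported measures of impulsivity and delayed discounting". Arm appears in neither sentence.

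The survey that supplies these answers is described under Administration of Surveys and/or Process. It follows each breath test, "which will include Perceived Driver Fitness and Perceived intoxication and BAC estimation, which are measured using a visual analogue scale". In the intervention group, "participants will be shown their BrAC readings on the BacTrack mobile app before completing their Self-Report of Intoxication Survey". The description of Arm 2 under Group Modifications gives the same order: "They will be shown their breath alcohol readings with the BACtrack Mobile Pro device before completing a visual analog scale". Controls stay blinded. The displayed reading and the measured BrAC come from the same BACtrack Mobile device.

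The Analysis Plan brings in arm for the primary outcome: "We will test for differences in perceived fitness to drive according intervention arm and BrAC level", with allowance for repeated readings within a participant and for time since the first drink. Its secondary paragraph reads: "We will conduct descriptive analyses exploring the effect modification of baseline demographic and psychological measures on these differences". It does not mention predicted BAC or self-reported intoxication.

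**The concern.** For the predicted-BAC item, one arm has been shown the comparator just before answering. A single association over all participants would mix unaided guesses with answers informed by the reading. It could not be read as people's ability to judge their own BAC, because about half the data would be aided. Nor would it show what the display does, because that needs the arms compared.

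Perceived intoxication is not a copy of the reading, but it too is answered under two information conditions. The secondary paragraph names impulsivity and delay discounting as modifiers and leaves out the one factor that was randomised, so a literal reading permits pooling. At stake is how a descriptive result from this pilot would be read by those planning a later study.

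**Working it through.** **What the plan fixes.** It gives no correlation, SD, effect size or allocation ratio for this analysis, so there is no figure to reproduce. The question is first one of reading.

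| Self-report item | Answered after the display in the intervention arm? | Arm handling stated? |
|---|---|---|
| Perceived fitness to drive | Yes | Yes, in the primary model with arm and BrAC level |
| Predicted BAC | Yes | No |
| Self-reported intoxication | Yes | No |
| Willingness to drive | Depends on a survey attachment not available here | No |

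The gap is therefore firm for predicted BAC, weaker for self-reported intoxication, and already covered for perceived fitness. The phrase about measurement by device does not settle it: whether it means as measured by the device or separately for each device, it is not stratification by arm. The secondary paragraph of the Analysis Plan does refer back to arm differences, but only those in perceived fitness.

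**What pooling could do (all inputs assumed).** Let r0 and r1 be the correlations of answer with BrAC in the blinded and displayed arms, and d the between-arm shift in mean answer in within-arm SDs. Assume equal arms, the same BrAC mean and SD in both (same dosing, randomised), and equal within-arm SDs of the answers. The pooled covariance, in SD units, is (r0 + r1)/2. The pooled variance of the answers is 1 + d²/4. Hence

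pooled r = [(r0 + r1)/2] / √(1 + d²/4).

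With r1 = 0.9:

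| r0 | d = 0 | d = 1 | d = 2 |
|---|---|---|---|
| 0.3 | 0.60 | 0.54 | 0.42 |
| 0.5 | 0.70 | 0.63 | 0.49 |
| 0.7 | 0.80 | 0.72 | 0.57 |

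For example, with r0 = 0.5 and d = 1: 0.70/√1.25 = 0.63. If r0 = r1 = 0.5 and only the mean shifts by d = 1, the result is 0.5/√1.25 = 0.45. At d = 2, the values for r0 = 0.5 and 0.7 fall below both arms' own correlations, so even the direction of the distortion is not fixed.

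Unequal spread changes little. If the displayed-arm SD is 0.7 times the blinded SD, with r0 = 0.5, r1 = 0.9 and d = 0, the covariance is (0.5 + 0.9 × 0.7)/2 = 0.565, the pooled SD is √[(1 + 0.49)/2] = 0.863, and r = 0.565/0.863 = 0.65.

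A separate simulation used 15 per arm and 9 readings each, with displayed-arm answers close to the reading. With a control calibration slope of 0.5 it gave correlations of 0.415 in controls, 0.991 in the displayed arm and 0.651 pooled.

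**What a mandatory split would cost.** Assume 30 enrol, 1:1, with one value per participant. The 95% half-width for a mean is t/√n: 2.145/√15 = 0.55 SD per arm, against 2.045/√30 = 0.37 SD overall, about 48% wider. For a correlation of 0.5, Fisher's z (0.549 ± 1.96/√(n − 3)) gives −0.02 to 0.81 with 15 and 0.17 to 0.73 with 30. Repeated readings would add some information; that gain is not computed here.

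**The case for a change.** The strongest case for a change is that one sentence would close the gap at almost no cost. Arm is known for every observation, and writing the rule down in advance stops the choice being made after results are seen. The primary hypothesis itself expects lower perceived fitness among those shown readings when BAC exceeds 0.05, so the sponsor already expects answers to depend on the display. The Abstract also hopes that "personal breathalyzers may reduce the risk of driving impaired by taking the guesswork out of estimating" one's own BAC.

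Part of this stands. The plan is silent on arm for predicted BAC and self-reported intoxication, and a pooled figure presented as unaided judgement would mislead.

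The rest is weaker. The Abstract sentence is about consumers using the devices and makes no prediction about the survey item. The hypothesis concerns perceived fitness, which is modelled with arm. A rule to report everything by arm would also add no between-arm contrast, so it would still not deliver the display effect. Applied to effect modification, it would split exploratory analyses into groups of about 15. A model with an arm-by-BrAC term that allows for repeated readings would keep all participants, and the present wording already permits it.

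**Conclusion.** No change to the plan follows. This is missing detail that analysts would fill sensibly: in a two-arm trial whose purpose is to compare shown with blinded participants, describing self-reports by arm is the natural course, and nothing in the text directs otherwise. Harm would need two further steps: someone pools the arms, and someone then reads the pooled predicted-BAC association as unaided accuracy or as a display effect. The plan promises only an association.

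The size is unknown. The pooled correlations above, from 0.42 to 0.80, rest wholly on assumed arm correlations and mean shifts and apply only to a raw pooled Pearson correlation. They show that a mixture can differ from its components, not that a planned result is wrong. The conclusion assumes that predicted blood alcohol content means the participant's own estimate in the survey, a term the plan does not define. Whoever reports these descriptive results should show them by arm and take any statement about unaided estimation from the blinded arm; the plan as written allows both.
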